### **11.2.2 Analysis of Secondary Efficacy Endpoints**

- Mean TETRAS-PS total score change from Baseline over 14 days.
- Mean TETRAS-PS upper limb subscale score change from Baseline over 14 days.
- Mean in-clinic wearable sensor measures of upper-limb tremor change from Baseline severity, mean amplitude, and mean frequency over 14 days.

Commercially Confidential Information

### **11.2.4 Sample Size Determination**

Approximately 30 subjects will be enrolled. No formal statistical power analysis was conducted. Each subject will be assessed for change from their own Baseline.

## **12 DATA MANAGEMENT AND RECORD KEEPING**

### **12.1 Data Management**

#### **12.1.1 Data Handling**

Data will be recorded at the site on eCRFs and reviewed during monitoring visits. Selected data recorded in the eCRF system will be verified with source documents. All corrections or changes made to any study data must be appropriately tracked in an audit trail in the EDC system. An eCRF will be considered complete when all missing, incorrect, and/or inconsistent data has been accounted for.

#### **12.1.2 Computer Systems**

Data will be processed using a validated computer system conforming to regulatory requirements.

#### **12.1.3 Data Entry**

Data must be recorded using the EDC system as the study is in progress. All site personnel must log into the system using their secure username and password in order to enter, review, or correct study data. These procedures must comply with Title 21 of the Code of Federal Regulations (21 CFR Part 11) and other appropriate international regulations. All passwords will be strictly confidential.

#### **12.1.4 Medical Information Coding**

For medical information, the following thesauri will be used:

- Medical Dictionary for Regulatory Activities (latest) for medical history and AEs
- World Health Organization Drug Dictionary CCI and concomitant medications

#### **12.1.5 Data Validation**

Validation checks programmed within the EDC system, as well as supplemental validation performed via review of the downloaded data, will be applied to the data in order to ensure accurate, consistent, and reliable data. Data identified as erroneous, or data that are missing, will be referred to the investigative site for resolution through data queries.

The eCRFs must be reviewed and electronically signed by the Investigator.

## **12.2 Record Keeping**

Records of subjects, source documents, monitoring visit logs, eCRFs, inventory of study product, regulatory documents, and other Sponsor correspondence pertaining to the study must be kept in the appropriate study files at the site. Source data is defined as all information in original records and certified copies of original records of clinical findings, observations, or other activities in a clinical study necessary for the evaluation and reconstruction of the clinical study. Source data are contained in source documents (original records or certified copies). These records will be retained in a secure file for the period as set forth in the Clinical Study Agreement. Prior to transfer or destruction of these records, the Sponsor must be notified in writing and be given the opportunity to further store such records.

## **12.3 End of Study**

The EOS (“study completion”) is defined as the date of the last protocol-specified visit/assessment (including telephone contact) for the last subject in the study.

## **13 INVESTIGATOR REQUIREMENTS AND QUALITY CONTROL**

### **13.1 Ethical Conduct of the Study**

Good Clinical Practice (GCP) is an international ethical and scientific quality standard for designing, conducting, recording, and reporting studies that involve human subjects. Compliance with this standard provides public assurance that the rights, safety, and wellbeing of study subjects are protected, consistent with the principles that have their origin in the Declaration of Helsinki, and that the clinical study data are credible.

### **13.2 Institutional Review Board/Independent Ethics Committee**

The Institutional Review Board (IRB) will review all appropriate study documentation in order to safeguard the rights, safety, and well-being of subjects. The study will only be conducted at sites where IRB approval has been obtained. The protocol, Investigator's Brochure, ICF, advertisements (if applicable), written information given to the subjects, safety updates, annual progress reports, and any revisions to these documents will be provided to the IRB by the Investigator.

Federal regulations and International Council for Harmonization (ICH) Guidelines require that approval be obtained from an IRB prior to participation of subjects in research studies. Prior to study onset, the protocol, any protocol amendments, ICFs, advertisements to be used for subject recruitment, and any other written information regarding this study to be provided to a subject or subject's legal guardian must be approved by the IRB.

No drug will be released to the site for dosing until written IRB authorization has been received by the Sponsor or designee.

### **13.3 Informed Consent**

The ICF and any changes to the ICF made during the course of the study must be agreed to by the Sponsor or designee and the IRB prior to its use and must be in compliance with all ICH GCP, local regulatory requirements, and legal requirements.

The Investigator must ensure that each study subject is fully informed about the nature and objectives of the study and possible risks associated with participation and must ensure that the subject has been informed of his/her rights to privacy. The Investigator or designee will obtain written informed consent from each subject before any study-specific activity is performed and should document in the source documentation that consent was obtained prior to enrollment in the study. The original signed copy of the ICF must be maintained by the Investigator and is subject to inspection by a representative of the Sponsor, their representatives, auditors, the IRB and/or regulatory agencies. A copy of the signed ICF will be given to the subject.

### **13.4 Study Monitoring Requirements**

It is the responsibility of the Investigator to ensure that the study is conducted in accordance with the protocol, Declaration of Helsinki, ICH GCP, and applicable regulatory requirements, and that valid data are entered into the eCRFs.

To achieve this objective, the monitor's duties are to aid the Investigator and, at the same time the Sponsor in the maintenance of complete, legible, well organized and easily retrievable data. Before the enrollment of any subject in this study, the Sponsor or their designee will review with

the Investigator and site personnel the following documents: protocol, Investigator's Brochure, eCRFs and procedures for their completion, informed consent process, and the procedure for reporting SAEs.

The Investigator will permit the Sponsor or their designee to monitor the study as frequently as deemed necessary to determine that data recording and protocol adherence are satisfactory. During the monitoring visits, information recorded on the eCRFs will be verified against source documents and requests for clarification or correction may be made. After the eCRF data is entered by the site, the monitor will review the data for safety information, completeness, accuracy, and logical consistency. Computer programs that identify data inconsistencies may be used to help monitor the clinical study. If necessary, requests for clarification or correction will be sent to Investigators. The Investigator and his/her staff will be expected to cooperate with the monitor and provide any missing information, whenever possible.

All monitoring activities will be reported and archived. In addition, monitoring visits will be documented at the investigational site by signature and date on the study-specific monitoring log.

### **13.5 Disclosure of Data**

Data generated by this study must be available for inspection by the FDA, the Sponsor or their designee, applicable foreign health authorities, and the IRB as appropriate. Subjects or their legal representatives may request their medical information be given to their personal physician or other appropriate medical personnel responsible for their welfare.

Subject medical information obtained during the study is confidential and disclosure to third parties other than those noted above is prohibited.

### **13.6 Retention of Records**

To enable evaluations and/or audits from regulatory authorities or the Sponsor, the Investigator will keep records, including the identity of all participating subjects (sufficient information to link records, e.g., eCRFs and hospital records), all original signed ICFs, copies of all eCRFs, SAE forms, source documents, and detailed records of treatment disposition. The records should be retained by the Investigator according to specifications in the ICH guidelines, local regulations, or as specified in the Clinical Study Agreement, whichever is longer. The Investigator must obtain written permission from the Sponsor before disposing of any records, even if retention requirements have been met.

If the Investigator relocates, retires, or for any reason withdraws from the study, the Sponsor should be prospectively notified. The study records must be transferred to an acceptable designee, such as another Investigator or another institution.

### **13.7 Publication Policy**

Following completion of the study, the data may be considered for publication in a scientific journal or for reporting at a scientific meeting. Each Investigator is obligated to keep data pertaining to the study confidential. The Investigator must consult with the Sponsor before any study data are submitted for publication. The Sponsor reserves the right to deny publication rights until mutual agreement on the content, format, interpretation of data in the manuscript, and journal selected for publication are achieved.

### **13.8        Financial Disclosure**

Investigators are required to provide financial disclosure information to the Sponsor to permit the Sponsor to fulfill its obligations under 21 CFR Part 54. In addition, Investigators must commit to promptly updating this information if any relevant changes occur during the study and for a period of 1 year after the completion of the study.

## **14 STUDY ADMINISTRATIVE INFORMATION**

### **14.1 Protocol Amendments**

Any amendments to the study protocol will be communicated to the Investigators by the Sponsor or designee. All protocol amendments will undergo the same review and approval process as the original protocol. A protocol amendment may be implemented after it has been approved by the IRB, unless immediate implementation of the change is necessary for subject safety. In this case, the situation must be documented and reported to the IRB within 5 business days.

## APPENDIX A: SCHEDULE OF ASSESSMENTS

Table 2: Schedule of Assessments

ASSESSMENTS	SCREENING	BASELINE	TREATMENT								FOLLOW-UP
	14-35 days prior to Day 1	Pre-dose  ( $\leq 3$ days prior to Day 1) (In-clinic)	Day 1  (In-clinic: Pre-Dose 1)	Day 1  (In-clinic: Dosing & Post-Dose 1)	Day 1  (In-clinic: Dosing & Post Dose 2)	Days 2-6 (At-home)	Day 7  (-1 day) (In-clinic)	Days 8-13 (At-home)	Day 14  ( $\pm 1$ day) / Early Termination  (In-clinic)	Days 15-20 (At-home)	
Eligibility Check	X	X									
Informed Consent	X										
Inclusion/Exclusion Criteria	X	X									
Demographics	X										
Medical History	X										
Neurological Exam	X 	X					X		X		X
Physical Exam	X	X 	X				X		X		X 
Height	X										
Weight CCI	X 								X		X
12-lead ECG 	X	X	X 	X  (30 min, 60 min, 2 hours post 1 st dose)	X  (30 min, 60 min, 2 & 4 hours post 2 nd dose)		X  (30 min, 60 min, 2 & 4 hours post 2 nd dose)		X  (30 min, 60 min, 2 & 4 hours post 2 nd dose)		X
Vital Signs 	X	X	X 	X  (30 min, 60 min, 2 hours post 1 st dose)	X  (30 min, 60 min, 2 & 4 hours post 2 nd dose)		X  (30 min, 60 min, 2 & 4 hours post 2 nd dose)		X  (30 min, 60 min, 2 & 4 hours post 2 nd dose)		X

**Table 2: Schedule of Assessments**

ASSESSMENTS	SCREENING	BASELINE	TREATMENT								FOLLOW-UP
	14-35 days prior to Day 1	Pre-dose  ( $\leq 3$ days prior to Day 1) (In-clinic)	Day 1  (In-clinic: Pre-Dose 1)	Day 1  (In-clinic: Dosing & Post-Dose 1)	Day 1  (In-clinic: Dosing & Post Dose 2)	Days 2-6 (At-home)	Day 7  (-1 day) (In-clinic)	Days 8-13 (At-home)	Day 14  ( $\pm 1$ day) / Early Termination  (In-clinic)	Days 15-20 (At-home)	Day 21  ( $\pm 1$ day) (In-clinic)
Orthostatic VS 	X (3 times, 15-20 min apart)	X		X (2-4 hours post 1 st dose)	X (2-4 hours post 2 nd dose)		X (2-4 hours post dose)		X (2-4 hours post dose)		X
Clinical Chemistry	X	X			X 		X 		X 		X
Hematology	X	X			X 		X 		X 		X
Urinalysis 	X	X			X 		X 		X 		X
Biomarker panel for renal tubular injury		X			X 		X 		X 		X
Pregnancy Test	X 	X 					X 		X 		X 
HIV, CCI HBsAg, HCVAb	X										
TSH – FSH (optional for females only; if needed)	X										

Commercially Confidential Information

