## **7.10       Orthostatic Vital Signs**

Orthostatic vital signs will be measured at Screening, Baseline, Day 1, Day 7, Day 14 and during the Follow-up visit.

During the Screening visit, orthostatic VS measurements will be done once, at any time during the visit.

During the Baseline/Pre-Dose visit, baseline orthostatic VS will include 3 separate measurements with each measurement of blood pressure and heart rate separated from the next by at least 15-20 minutes apart, to minimize the potential impact of biological variability of a single baseline measurement. The average of the 3 baseline orthostatic VS measurements will be used for comparison to all post-treatment measurements.

During Day 1, orthostatic VS measurements will be done twice, 2 to 4 hours following each in-clinic dose.

During Day 7 and Day 14 visits, orthostatic VS measurements will be done once, 2 to 4 hours following the in-clinic dose.

During the Follow-up visit, orthostatic VS measurements will be done once, at any time during the visit.

Orthostatic VS must be assessed using an appropriate device, and the arm position must be standardized for each subject. These measurements are to be taken in the same arm for the duration of the study. The position of the cuff on the arm should be in line with the heart with the arm lying next to the subject when semi-supine and should be in line with the heart at approximately a 45 degrees angle from horizontal for the standing measure.

In order to obtain orthostatic VS, the subjects will undergo the following procedures in sequential order:

1. The subject will rest in a supine or semi-supine position for at least 5 minutes.
2. After remaining supine or semi-supine for 5 minutes, one measurement of blood pressure and heart rate will be taken.
3. The subject will then be asked to sit on the edge of the bed/chair with feet on the floor (or with feet dangling from the bed/chair depending on the height of the bed/chair) for approximately 30 seconds.
4. The person performing the assessment will then ask the question, “Are you ready to stand?”
  - If the subject responds in the affirmative, the subject will proceed to stand and then be asked to remain standing for 2 minutes. After standing for 2 minutes, blood pressure and heart rate will be recorded.

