**Schedule of Assessment Footnotes:**

 The Baseline/Pre-dose visit is the last day of the Screening period. The Baseline/Pre-dose visit must be conducted in the afternoon.

 Commercially Confidential Information

 In addition to the complete neurological exam, a focused neurological exam is conducted during the Screening visit to include full assessment of tremor per Movement Disorder Society classification criteria ([Bhatia, 2018](#)).

 Complete PE at Screening, Days 1, 7, and 14 (includes: General; HEENT; Cardiovascular; Respiratory; Abdomen; Skin; Extremities; Lymphatic system and Musculoskeletal); symptom-based PE at Baseline/Pre-dose and Day 21 Follow-up visit (includes: General, HEENT, Cardiovascular, Respiratory, Abdomen, Skin, Extremities).

 Commercially Confidential Information

 Triplicate ECG recordings, after a minimum of 5 minutes of rest in supine position: 3 consecutive recordings will be made in succession, no more than 2 minutes apart. The full set of triplicates should be completed in less than 4 minutes. These ECGs will be read by the Investigator to rule out any clinically significant findings. ECGs are to be performed prior to vital signs and blood sampling.

 Blood pressure (systolic and diastolic), heart rate, respiratory rate and oral temperature.

 Obtained prior to dosing and post dosing at 30min, 60min, 2 hours and 4 hours following the dose of study drug in the clinic. For Day 1, this is to be done Baseline/Pre-dose and 30min, 60min, and 2 hours after the first dose in the clinic, and again 30 min, 60 min, 2 hours, and 4 hours after the second dose in the clinic. There is a +/- 5-minute allowable time window for these assessments. ECG to be done before the corresponding vital sign measurements.

 For details re: orthostatic vital signs measurements, refer to Section 7.10.

 Urinalysis includes: Bilirubin, Blood, Creatinine, Glucose, Ketones, Leukocyte esterase, Microscopy, Nitrite, pH, Protein, Specific gravity, Microalbumin and Urobilinogen

 A serum pregnancy test is done at Screening only.

 A urine pregnancy test is done at Baseline/Pre-dose, Days 7, 14, and 21.

 Commercially Confidential Information

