## 6. General Considerations for Statistical Analysis

### 6.1. Statistical Definitions and Algorithms

#### 6.1.1. Baseline

The last non-missing observed value recorded on or before the date of the first dose of treatment at the Pre-dose visit will be used as the baseline observation for all calculations of change from baseline.

Wearable sensor measurements of upper limb tremor will be captured at 2 different times during the Pre-dose visit (Visit 2); the average of the 2 assessments will be used as the baseline observation for all calculations of change from baseline in wearable sensor assessments.

During the Pre-dose visit, baseline orthostatic vital signs will include 3 separate measurements, and the average of the 3 (or fewer if missing data occur) baseline orthostatic vital signs measurements will be used as baseline for comparison to all post-treatment measurements.

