### 9.3. Vital Signs

Descriptive summaries of observed values and changes from baseline will be calculated for supine systolic blood pressure (SBP), standing SBP, supine diastolic blood pressure (DBP), standing DBP, supine heart rate (HR), standing HR, respiration rate, and oral temperature by study visit for the Safety Population overall and by cohort. Shifts from baseline for SBP, DBP, and HR values below, within, or above the normal range will be provided by study visit for the Safety Population overall and by cohort. Vital sign parameters outside the normal range will be flagged in the listings. The mean change from baseline in each parameter will also be plotted by study visit. Abnormal vital signs are as follows:

Commercially Confidential Information

- SBP >140 mmHg
- SBP <90 mmHg
- DBP >90 mmHg
- DBP <60 mmHg
- HR >100 bpm
- HR <60 bpm
- Respiration rate >20 breaths/min
- Respiration rate <12 breaths/min
- Oral temperature >99.1 °F/37.2 °C
- Oral temperature <97.8 °F/36.5 °C

Orthostatic vital signs (blood pressure and heart rate) will also be summarized by position and study visit and by cohort. During the Pre-dose visit, baseline orthostatic vital signs will include 3 separate measurements and the average of the 3 baseline orthostatic vital signs measurements will be used for comparison to all post-treatment measurements. The average HR, SBP, and DBP will be presented in the pre-dose baseline summaries and each of the individual measurements will be listed for that study visit.

Orthostatic hypotension will be defined as a reduction in systolic blood pressure of 20 mmHg or more and/or a reduction in diastolic blood pressure of 10 mmHg or more, for the standing measurement compared to the supine or semi-supine measurement. The frequency and percentage of subjects with orthostatic hypotension will also be presented by cohort. Any confirmed orthostatic hypotension or clinically significant measurements that are associated with clinical symptoms will be recorded as AEs. Orthostatic vital signs parameters outside the ranges specified above will be flagged in the listings.

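### Both schedules place the triplicate orthostatic readings under Screening, while Protocol Section 7.10 and the SAP baseline definition place them at Baseline/Pre-dose

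*Protocol*

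**What the plan says.** Four places bear on the number of orthostatic readings before dosing.

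- **Schedules.** In Protocol Appendix A, Table 2, the orthostatic row has "X (3 times, 15-20 min apart") under Screening and a bare X under Baseline. SAP Section 3.7, Table 1 repeats both cells. Footnote 9 on that row says: "For details re: orthostatic vital signs measurements, refer to Section 7.10".
- **Protocol Section 7.10.** For Screening: "During the Screening visit, orthostatic VS measurements will be done once, at any time during the visit". For Baseline: "During the Baseline/Pre-Dose visit, baseline orthostatic VS will include 3 separate measurements". The section gives its reason, which is to limit the effect of biological variability in a lone baseline value, and adds: "The average of the 3 baseline orthostatic VS measurements will be used for comparison to all post-treatment measurements".
- **SAP Section 6.1.1.** "During the Pre-dose visit, baseline orthostatic vital signs will include 3 separate measurements", and then "the average of the 3 (or fewer if missing data occur) baseline orthostatic vital signs measurements will be used as baseline".
- **SAP Section 9.3.** "the average of the 3 baseline orthostatic vital signs measurements will be used for comparison to all post-treatment measurements".

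The SAP table shells are not uniform. The footnote to Table 14.3.6.1.6 uses the average of three. The footnote to Table 14.3.6.1.5 uses the last observation before the first dose. Tables 14.3.6.1.3 and 14.3.6.1.4 reuse laboratory shells that carry the same last-observation footnote, and their programming notes do not replace it.

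**The concern.** The schedule is an instruction to sites. Protocol Section 6 calls adherence to it essential, and Section 6.1.2 has the Baseline procedures done as the schedule indicates. Section 7.10 is also an instruction, and the two disagree. At Screening the conflict is explicit: three readings against one. At Baseline it is three against an X with no number.

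What is at stake is the precision of the orthostatic baseline. If a site took one reading at Baseline, the missing-data allowance in SAP Section 6.1.1 would let the analysis go ahead on that reading. The analysis would then rest on the single measurement that Section 7.10 sets out to avoid, and the three Screening readings would have no role in the baseline. Safety and tolerability are the primary objective, and orthostatic vital signs are among the planned safety summaries.

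**Working it through.** **1. Is a shifted column the explanation?** The table has 11 data columns: Screening; Baseline; Day 1 before dose 1; Day 1 after dose 1; Day 1 after dose 2; Days 2-6; Day 7; Days 8-13; Day 14/Early Termination; Days 15-20; Day 21. The orthostatic row has 11 cells.

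| Column | Schedule cell | Section 7.10 | Agree? |
|---|---|---|---|
| Screening | three readings | one reading | No |
| Baseline | X, no count | three readings | Not on the natural reading |
| Day 1 after dose 1 | 2-4 h after dose | 2-4 h after dose | Yes |
| Day 1 after dose 2 | 2-4 h after dose | 2-4 h after dose | Yes |
| Day 7 | 2-4 h after dose | once, 2-4 h after dose | Yes |
| Day 14 | 2-4 h after dose | once, 2-4 h after dose | Yes |
| Day 21 | X | once | Yes |

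The remaining four columns are empty in the schedule and are not mentioned in Section 7.10. A shift of the whole row would have moved the later cells too. Only the first two disagree.

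**2. What would one reading instead of three cost?** The documents give no variance for orthostatic measurements, so this step rests on assumptions. Let sw² be the variance of a single reading within a visit, sb² the visit-to-visit variance within a subject, m the number of Baseline readings, and r = sb²/sw². Assume one post-dose reading with the same variances, and independent errors. Then

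Var(change) = 2·sb² + sw²·(1 + 1/m).

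The SD with m = 1 relative to m = 3 is therefore

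√[(2r + 2) / (2r + 4/3)].

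| r (assumed) | Variance ratio | SD ratio | Increase in SD |
|---|---|---|---|
| 0 | 2/1.333 = 1.500 | 1.225 | about 22% |
| 0.5 | 3/2.333 = 1.286 | 1.134 | about 13% |
| 1 | 4/3.333 = 1.200 | 1.095 | about 10% |
| 3 | 8/7.333 = 1.091 | 1.044 | about 4% |

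The figure for r = 0 is a ceiling. Baseline and treatment visits fall on different days, so some visit-to-visit variance is to be expected.

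**3. Which outputs depend on the Baseline count?**

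- *Dependent:* change-from-baseline summaries (Table 14.3.6.1.3), range shifts referenced to baseline (Table 14.3.6.1.4), and the Baseline row of the orthostatic hypotension table (Table 14.3.6.1.6).
- *Not dependent:* orthostatic hypotension after dosing. Protocol Section 7.10 and SAP Sections 6.1.8 and 9.3 define it as standing against supine or semi-supine at the same assessment. The shift status in Table 14.3.6.1.5 is also standing against supine, despite its title and baseline footnote.

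**The case against.** The strongest reply is that this is a clerical slip that the plan already neutralises. Footnote 9 sends the reader to Section 7.10, which is explicit and gives its reason. Protocol Section 6.4 has assessments done both as the schedule indicates and as Section 7 describes. Nor does a bare X in this table always mean one: the Baseline ECG cell is a bare X, and footnote 6 makes it three recordings. A site following both texts might take three readings at Baseline and, at worst, extra ones at Screening.

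Much of this stands. A reader might infer that subjects did have only one Baseline reading, but the cell states no number and the documents do not establish that. The literal reading is still a natural one. In the same row the bare X at Day 21 is a single reading, and a count is written out where three are meant. Footnote 9 exposes the conflict but does not remove it, since Section 7.10 asks for one reading at Screening where the cell says three.

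Three further inferences go too far:

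- **That the loss would go unseen.** SAP Section 9.3 has the individual Pre-dose measurements listed, and Listing 16.2.8.3.2 has a column for the measurement number and the total.
- **That the SD rises by a flat 22%.** This needs zero between-visit variance.
- **That post-dose orthostatic hypotension would be over-counted.** Its definition does not use the Baseline readings.

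It can also be said that the SAP table is a copy of the protocol's, so their agreement is not independent evidence against a text-extraction fault. That is fair. The better evidence is that the other cells of the row align.

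**Conclusion.** The contradiction is real and should be corrected. Both schedules put the triplicate at Screening, while Section 7.10 and SAP Sections 6.1.1 and 9.3 put it at Baseline/Pre-dose. It is an inconsistency in an operational instruction rather than a fault of design.

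The consequence is conditional and modest. If a site took one Baseline reading, the SD of change from baseline in orthostatic vital signs would rise by about 4% to 22% over the assumed variance ratios of 3 down to 0. The affected outputs are descriptive, in about 30 subjects. The post-dose hypotension counts stand either way.

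**What to change.** - **Schedules.** Reconcile the orthostatic row in Protocol Table 2 and SAP Table 1 with Protocol Section 7.10 and SAP Sections 6.1.1 and 9.3, so that the visit with triplicate readings is the visit whose average is the analysis baseline. The sponsor should decide the number of readings at each visit and state it the same way everywhere.
- **Shells.** Align the baseline footnote of Table 14.3.6.1.5, and the one that Tables 14.3.6.1.3 and 14.3.6.1.4 inherit, with the definition in SAP Section 6.1.1.
- **Reporting.** Use the existing count column in Listing 16.2.8.3.2 to identify subjects whose baseline rests on fewer than three readings, and report how many there are.

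The cost is one row in each schedule, a few footnotes and a count from a column already planned. The protocol edit goes through the usual amendment route. If the data are already collected, the schedule correction cannot change them, but the shell alignment and the count remain useful.
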